This study (Figures 1 and 3) will include Option A consisting of 9 lab visits each approximately 2 hours long, except visit 1, which will last up to 3 hours **OR** Option B consisting of 5 lab visits each containing 2 vaping sessions separated by a 3-hour washout period and lasting approximately 6 hours. Figure 2 illustrates the study e-cig and e-liquid variations. Figure 3 depicts the sequence of the proposed study. We will conduct an experimental study examining how the manipulation of nicotine form (nicotine salt (NSB) vs. free-base (FB)) influences vaping behavior, abuse liability, toxicant exposure and heart and lung health.

Evaluating E-Cigarette Nicotine Form, Concentration, and Flavors among Youth

Figure 1. Vaping Session

Vaping Session	
12 hour nicotine abstinence	
Start of Session:	Surveys Respiratory Measures Cardiovascular Measures Blood Draw (0 min)
STD Puffing (5 min):	Blood Draw (5 min) Surveys
Ad-lib Puffing (30 min): Blood Draw (10 min) Blood Draw (35 min) Surveys	
3-hour washout (Visits 2-5 between vape sessions) (Option B Only)	
3 hrs. post exposure:	Respiratory Measures Cardiovascular Measures (Option B Only)
1 vaping session will occur at each visit for 9 visits (Option A Only)	
1 vaping session will occur at the first visit / 2 vaping sessions will occur at the final 4 visits (Option B Only)	

Figure 2. E-cig and e-liquid for Vaping Sessions

[figure not shown]
[figure not shown]

Figure 3. Study Sequence Option A and Option B

Evaluating E-Cigarette Nicotine Form, Concentration, and Flavors among Youth

ii. Study Procedures

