Utilizing a within-subjects, factorial design, 60 e-cig users (aged 21-25 years) will complete vaping sessions which will include a standardized, 5-minute, 10-puff vaping bout (30 seconds between each puff) followed by 30 minutes of ad libitum vaping. Prior to session one, participants will be asked to bring their own e-cig device and a full tank/pod to the first visit. In session one, participants will use their own e-cig and e-liquid. After visit 1, participants will take home a study e-cig device and 1 weighed pod pre-filled with study e-liquid (the participant was randomized to at the end of visit 1) to practice (20 puffs per day with the study device and until the participant feels comfortable) using the device before visit 2. Practice use with the study e-cig device and pre-filled pod will be verified based on data downloaded (via eScribe) from the device during visit 2. In the subsequent vape sessions, participants will use a study e-cig held at a constant wattage, and pre-filled with e-liquid of different nicotine form (free-base vs. nicotine salt), concentration (low-1% vs. high-5%), and flavoring (tobacco vs. menthol). There is no known commercial pair of nicotine liquids that differ only by nicotine form. For this study, we will prepare 8 e-liquids that differ by nicotine form, nicotine concentration, and flavor, simulating characteristics of popularly used nicotine liquids^{32,39}. E-liquids will be prepared from pure ($\geq 99\%$) S-(-)-nicotine; protonation and dilution of nicotine will be done using USP grade benzoic acid, and glycerol and propylene glycol, respectively. We will submit an Investigational Tobacco Product application to the U.S. FDA regarding the clinical use of the e-liquids. All sessions will be completed over nine visits for schedule Option A and 5 visits for schedule Option B. Study Schedule A consist of 9 separate visits and 9 separate vaping sessions. Study schedule B will consist of five separate visits (each visit will include up to 2 vaping sessions) each separated by a 3-hour washout period to allow nicotine levels to return to baseline. Each visit will be at least 48 hours apart. Participants will be required to report at least 12 hours abstinent from nicotine before each study visit. Participants will be told that their abstinence will be confirmed at the time of visit via blood plasma nicotine analysis. This is a partial bogus pipeline⁴⁰; 3mL venous blood sample will be collected for later analysis.; those with plasma nicotine levels $>3\text{ng/mL}$ at the time of their visit will be replaced post hoc with another participant. We conservatively estimate replacing 10% of participants. Measures of topography, nicotine uptake, abuse liability, subjective effects, and cardiovascular and pulmonary effects will be collected (see Table 1). Exposure to select toxicants, including nicotine and menthol in total particulate matter, and gas phase carbonyls and volatile organic compounds, will also be estimated post hoc using puff playback machine smoking.

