Participants' eligibility will be determined over the phone or via REDCap's online screener. Those who are eligible and willing to participate will be invited to sign an informed consent and complete their baseline visit in a private participant room at the Ohio State University. All participants will be given adequate time to review the informed consent with a trained research staff to help answer any questions that may arise during the consent process. Additionally, a copy of the informed consent will be given to all participants. A pregnancy test will be completed at the initial visit as well as before starting all the in-lab visits to ensure that the participant is not pregnant.

b) Retention and Compensation

If participants choose Option A, they will receive \$50, \$50, \$50, \$50, \$75, \$75, \$75, \$75, and \$100 for completing visit 1, 2, 3, 4, 5, 6, 7, 8, and 9, respectively, for a total of \$600. Participants who choose Option B will receive \$50, \$100, \$125, \$150, and \$175 for completing visit 1, 2, 3, 4 and 5, respectively, for a total of \$600. Consistent with our previous studies, payments will be made using the Greenphire ClinCard to increase accountability and facilitate ease of payment. We will facilitate visits by offering weekend appointments and using additional retention strategies (e.g., reminder calls/texts/emails). Participants will receive reminder calls in addition to email or text reminders. Reminders will be sent by text or email based on a participant's preferred method of contact.

2. Detailed Study Procedures

a) Study Sessions

Prior to the start of the first laboratory visit, twelve-hour tobacco abstinence will be assessed via self-report and confirmed with exhaled carbon monoxide testing ($eCO \leq 10$ ppm). A research assistant will

Evaluating E-Cigarette Nicotine Form, Concentration, and Flavors among Youth

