E-cig device characteristics, including device voltage, coil resistance, and pressure drop; and e-liquid characteristics including pH, nicotine concentration, and PG/VG ratio will be determined. Since participants will primarily use the study e-cig and e-liquid for this study, to determine exposures associated with the least and most intense puffing behaviors, topographies in the upper tertile will be averaged to produce a single topography, and likewise for the lowest tertile. Machine vaping will be conducted for each e-liquid type, using the associated human-derived puffing regimens, to estimate the range of tobacco toxicant exposure.

For the 8-test e-liquids, these measures will be repeated during each of the visits. Study schedule A consists of 9 separate visits and 9 separate vaping sessions. Study schedule B consists of 5 visits. The first lasting about 2 hours and the subsequent visits 2-5 lasting about 6 hours each, 2 vaping sessions each visit, and each session separated by a 3-hour washout period to allow nicotine levels to return to baseline.

After each visit has been completed, participants will sign to confirm they have received \$50, \$50, \$50, \$50, \$75, \$75, \$75, \$75, and \$100 for completing visit 1, 2, 3, 4, 5, 6, 7, 8, and 9, respectively, for a total of \$600 if they chose Option A or received \$50, \$100, \$125, \$150, and \$175 for completing visit 1, 2, 3, 4

Evaluating E-Cigarette Nicotine Form, Concentration, and Flavors among Youth

and 5, respectively, if they chose Option B. Participant compensation will be loaded on a Greenphire ClinCard.

b) Study Products

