Laboratory Spirometry (SpiroLab)	X	X
Airway Inflammation (NIOX VERO)	X	X
Airway Reactivity (TremoFlo)	X	X
Cardiovascular Measures		
Vascular Reactivity (Vicorder or similar)	X	X
Blood Pressure	X	X
Heart Rate	X	X
Markers of endothelial dependent and independent function		
B-mode ultrasound (Vicorder or similar)	X	X
Arterial stiffness		
Pulse wave velocity and analysis (Vicorder or similar)	X	X

Evaluating E-Cigarette Nicotine Form, Concentration, and Flavors among Youth

E. Statistical Methods

Generalized linear mixed models will be employed to identify associations of nicotine form, nicotine concentration, and flavoring with various outcome measures (e.g., plasma nicotine, spirometry, flow-mediated dilation). Models will include relevant covariates (e.g., gender), a random effect for participant, main effects for nicotine form and concentration, and the interaction between nicotine form and concentration and nicotine form and flavor. Because of multiple measurements tested, we will assume a significance threshold corresponding to one expected false discovery per 100 tests ($p=0.01$).

i. Power Analysis

This study, for each of the main effects and $\alpha = 0.01$, achieves 80% power to detect an effect size of 0.5 standard deviations of the paired differences. For interaction effects, we will estimate 80% power (effect size 0.5 SD) to distinguish between any two of the interaction groups (e.g., free base/low nic, free base/high nic), while correcting for the pairwise tests ($p=0.01/6=0.0017$). Carryover and period effects will also be examined.

ii. Data Analytic Plan

Because product sampling will be randomized using a Latin Square, a fixed effect for session and a random effect for sequence will be included in all analyses.

iii. Missing Data

While we will make every effort to minimize the missing data for this study, missing data can arise due to various reasons. Violation of missing complete at random (MCAR) will be checked by evaluating whether any covariates are associated with missing data. If so, these covariates will be subsequently included and controlled for in the GLMM model. Our primary analysis will use mixed models which assumes Missing At Random (MAR) to deal with the missing data problem. In addition, sensitivity analyses will also be conducted using results from multiple imputation and complete cases strategies.

F. Gender/Minority/Pediatric Inclusion for Research

i. Inclusion of Women and Minorities

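### Option B tests two liquids in one visit, but the model has no participant-by-visit term; if same-day sessions are correlated, precision is lost and standard errors depend on how liquids are paired

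*Combined protocol and SAP*

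**What the plan says.** The layout is in the Design Overview (D.i) and Study Procedures (D.ii). Figure 1 gives the Option B schedule as "1 vaping session will occur at the first visit / 2 vaping sessions will occur at the final 4 visits (Option B Only". D.ii describes "2 vaping sessions each visit, and each session separated by a 3-hour washout period to allow nicotine levels to return to baseline" and, for visits, "Each visit will be at least 48 hours apart". Option A has one session per visit. Participants pick the schedule themselves: the compensation text begins "Participants who choose Option B will receive". The expected split is not given.

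Section E lists the model: "Models will include relevant covariates (e.g., gender), a random effect for participant, main effects for nicotine form and concentration", followed by form-by-concentration and form-by-flavor interactions. E.ii adds that "product sampling will be randomized using a Latin Square" and that "a fixed effect for session and a random effect for sequence will be included in all analyses". E.i says that carryover and period effects will be examined. The type of Latin square is not stated, nor how liquids fall into same-day pairs. No robust standard error is mentioned.

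**The concern.** A participant's condition on a given day can shift both of that day's sessions together. Such a shift cancels when the two same-day liquids differ in nicotine form, and adds up when they share it. The listed terms cannot represent this. The session effect is a mean shift by order, common to all participants. If sequence means the Latin-square order, its effect is constant within a person. The participant effect treats all eight sessions as equally related.

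Two things are at stake. Comparisons made on the same day carry extra information that the model does not use. And the 0.01 threshold, set that low because many measures are tested, may not be the level at which the form test actually runs.

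**Working it through.** **Inputs from the documents.** Eight liquids; four Option B visits of two sessions after visit 1; 60 completers; alpha 0.01 (sidedness not stated, two-sided taken here); the model terms above.

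**Assumptions.** The documents give no visit-level variance and no Option B share. I take the participant-by-visit variance as 25%, 50% or 100% of the session residual. As a share of within-person variance, ρ = v/(1 + v) = 0.20, 0.33, 0.50. Normal approximation throughout.

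**The plan's own figure.** E.i states 80% power for 0.5 SD of the paired differences. With 60 completers, 0.5 × √60 = 3.873, and 3.873 − 2.576 = 1.297, giving 90.3% (88.3% with the t distribution). The stated 80% is therefore conservative for main effects. It does not separate same-day from different-day differences, so it does not bear on this point.

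**Step 1: variance the model reports.** Eight sessions form 28 pairs, of which 4 share a visit. The participant effect absorbs the average correlation, ρ × 4/28 = ρ/7. With within-person variance set to 1, the reported variance of the form effect is proportional to 1 − ρ/7.

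**Step 2: true variance.** The form effect for one person is the mean of four salt sessions minus the mean of four free-base sessions. A visit shift cancels if that visit holds both forms, and enters with weight 2/4 if it holds one form twice. With k one-form visits out of four, the true variance is proportional to (1 − ρ) + kρ/2. Under random pairing a liquid's partner has the same form with probability 3/7, so k averages 12/7. The variance is then 1 − ρ + 6ρ/7 = 1 − ρ/7, which equals the reported one.

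**Step 3: real alpha.** Real alpha = 2 × [1 − Φ(2.576 × R)], where R = √{(1 − ρ/7) / (1 − ρ + kρ/2)} is reported SE over true SE. In a cyclic 8 × 8 square with liquids listed in factorial order (four of one form, then four of the other), rows starting at an odd position have k = 4 and the rest k = 2, so k averages 3. The opposite extreme, both forms in every visit, has k = 0. All 60 on Option B:

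| Visit variance / residual | 1 − ρ/7 | True, k = 3 | R | Real alpha | True, k = 0 | R | Real alpha |
|---|---|---|---|---|---|---|---|
| 25% | 0.971 | 1.100 | 0.94 | 0.016 | 0.800 | 1.10 | 0.0045 |
| 50% | 0.952 | 1.167 | 0.90 | 0.020 | 0.667 | 1.20 | 0.0021 |
| 100% | 0.929 | 1.250 | 0.86 | 0.026 | 0.500 | 1.36 | 0.0004 |

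Now keep the cyclic square but assign liquids to its labels at random. Of the 70 ways to place four and four on the cycle, 8, 36, 24 and 2 give an average k of 3, 2, 1 and 0. The weighted mean real alpha is 0.0102, 0.0105 and 0.0112. The unfavorable pairing arises in 8/70 = 11% of labelings. With half on Option B and the factorial-order square, R² = (1 − ρ/14)/(1 + ρ/4), and real alpha runs from 0.013 to 0.017.

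**Step 4: information lost.** With random orders, 4/7 of the information on form lies within visits (variance 1 − ρ) and 3/7 between visits (variance 1 + ρ). Let I = (4/7)/(1 − ρ) + (3/7)/(1 + ρ) = 1.071, 1.179, 1.429. With a visit term the variance is 1/I = 0.933, 0.848, 0.700, against 0.971, 0.952, 0.929 without it. The saving is 3.9%, 10.9% and 24.6%; finite sets of random orders give about 4%, 10–11% and 24–25%. With half on Option B, 2/(1 + I) = 0.966, 0.918, 0.824 against 1 − ρ/14 = 0.986, 0.976, 0.964, a saving of about 2%, 6% and 15%.

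**The case against.** The strongest objection is that the inflated alpha is an unfavorable case. It needs a high Option B share, appreciable visit variance and a square left in factorial order, whereas E.ii says that product order is randomized. Under randomized labels or orders the standard error is about right on average. This stands. A reader might infer that the form test is anticonservative as planned; the documents do not support that, because they state neither the square, the share nor the variance.

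Four other inferences also go too far:

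- That a flavor test is over-conservative. Section E lists no flavor main effect; flavor enters only through its interaction with form.
- That the two sessions of a visit start from the same abstinence state. The first follows 12 hours without nicotine. The second follows nicotine exposure and a 3-hour washout in which eating and drinking are allowed. Nor do the documents say that equipment set-up is shared.
- That visits are ignored altogether. The fixed session effect largely takes up average differences between visits; what is missing is the participant-by-visit part.
- That same-day correlation must be positive. Satiation after the first liquid could make it negative for puffing, craving or liking, and a random intercept cannot represent that.

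A further caution also stands: same-day pairs are the pairs most exposed to carryover, and a visit term gives them more weight. None of this removes the gap. No listed term allows same-day covariance, and the stated carryover and period checks concern means.

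**Conclusion.** The gap is real, and its size is unknown from the documents. If same-day sessions are positively correlated, the more dependable consequence is lost precision: with random orders, about 4%, 10–11% and 25% of the variance of the form effect if all choose Option B, and roughly half that (2%, 6%, 15%) if half do. Wrong standard errors are possible in both directions. For form, a cyclic square in factorial order gives a real alpha of about 0.016 to 0.026, and a square that always pairs the two forms gives 0.0045 down to 0.0004. With randomized labels or orders the average is about nominal. All of these figures rest on the assumed visit variance and Option B share. With no same-day correlation, or with nobody on Option B, the planned model loses nothing here. This is an inexpensive correction to the specification, not evidence that the planned tests are invalid.

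**What to change.** In Section E, add to every model a random intercept for visit within participant. A within-visit residual covariance that can also be negative would serve better for outcomes where satiation is plausible. In Option A each visit has one session, so the term adds no same-day covariance there and those data are unaffected.

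In E.ii, state which Latin square is used and how it pairs liquids within Option B visits. Randomize the assignment of liquids to the square's labels, so that no factor is systematically tied to the visit. If the allocation list is already fixed, report the pairings it produced.

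The cost is one variance component and a few lines of text, with no change to sample size or visits. There are two downsides. The component may be estimated at zero, for example if few choose Option B or the correlation is negative; the model then reverts to the planned one. And same-day pairs gain weight, so the planned carryover check should be reported beside the main result.

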
1. Recruitment Feasibility and Retention

a) Recruitment

We intend to recruit 130 e-cig users from the community over an 18-month period and have them complete nine study visits (Option A) or five study visits (Option B); therefore, we need 3-4 participants to be recruited and complete study procedures per month.

We are confident our recruitment approach, laboratory facilities, and equipment redundancy will result in a sufficient participant processing rate, given our successful completion of other tobacco-related research of similar design⁴¹. E-cig users will be recruited from advertisements through a variety of media outlets and the internet, including Study Search, as well as community events. Participants from

Evaluating E-Cigarette Nicotine Form, Concentration, and Flavors among Youth

other studies who have agreed to be contacted regarding other study opportunities will also be contacted. Staff from those studies will prepare contact letters/emails and call participants on behalf of this study. Interested participants will be referred to this study for screening. Participants will access the screening questionnaire using a public survey link generated by REDCap. Based on our team's previous studies, we conservatively assume a 20% attrition rate. Thus, we need to recruit 130 participants to have 60 complete the study. Participants who meet the following eligibility criteria will be asked to take part in the study.

Inclusion criteria: 1) a current e-cigarette user (≥ 1 vaping bout per day) for at least the past 3 months , 2) 21-25 years old, 3) willing to abstain from all tobacco and nicotine for at least 12 hours prior to lab sessions, 4) willing to complete nine lab visits/vaping session lasting up to 2 hours each or five lab visits lasting up to 6 hours each (except Visit 1) , 5) able to read and speak English, 6) willing to provide informed consent

Exclusion criteria: 1) self-reported diagnosis of lung disease including asthma, cystic fibrosis, or chronic obstructive pulmonary disease, 2) history of cardiac event or distress within the past 3 months, 3) currently pregnant (determined using urine pregnancy test), planning to become pregnant, or breastfeeding, 4) use of other tobacco products >10 days in the past month, 5) current marijuana use >10 times per month, 6) currently engaging in a vaping cessation attempt.

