Markers of endothelial dependent and independent function will be measured by B-mode ultrasound⁴⁴. Arterial stiffness, blood pressure, and heart rate will be measured at baseline. Arterial stiffness and vascular reactivity will be measured with pulse wave velocity (Vicorder or similar) and pulsewave-analysis (AiX75, SphygmoCor, or similar)⁴⁵. Inflammation will be measured by plasma levels of IFN- β , IL-1 β , IL-17, TNF- α as well as markers of oxidative stress, including OxLDL and Malondialdehyde⁴⁶. Laboratory spirometry, airway inflammation, and airway reactivity⁴⁷⁻⁴⁹ will be measured. Laboratory Spirometry will be conducted in a standing position and according to the recommendations of ATS Clinical Guidelines⁴⁷. Forced expiratory volume (FEV1), forced vital capacity (FVC), and FEV1/FVC. Airway Inflammation will be assessed using exhaled nitric oxide via the NIOX VERO. The current literature shows immediate changes in airway inflammation immediately follow e-cig use⁴⁸. Airway Reactivity will be measured via TremoFlo, which is a well validated measurement of central obstruction, peripheral obstruction, and dynamic collapse⁴⁹ and provides curves of Resistance (R) and Reactance (X) as well as parameters reflecting large and small airway function. The current literature show an increase in impedance, respiratory resistance and overall peripheral airway resistance following e-cig use⁴⁸.

In visit 1, which will last up to 3 hours, participants will use their own e-cig and e-liquid and participate in a single vaping session. After visit 1, participants will take home a study e-cig device and 1 weighed pod pre-filled with tobacco flavored e-liquid (the participant is randomized to at the end of visit 1) to practice (20 puffs per day with the study device and until the participant feels comfortable) using the device before visit 2. Practice use with the study e-cig device and pre-filled pod will be verified based on data downloaded (via eScribe) from the device during visit 2. After visit 1, for the subsequent visits

Evaluating E-Cigarette Nicotine Form, Concentration, and Flavors among Youth

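### Section E does not specify adjustment for the pre-vaping heart or lung value taken at the start of each session, so H1b contrasts may give up precision wherever a post-vaping value exists

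*Combined protocol and SAP*

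**What the plan says.** Section A (H1b) predicts that form and flavor affect acute cardiovascular and pulmonary outcomes. Section E gives spirometry and flow-mediated dilation as examples of modelled outcomes and describes the model thus: "Models will include relevant covariates (e.g., gender), a random effect for participant, main effects for nicotine form and concentration". It adds the form-by-concentration and form-by-flavor interactions. Section E.ii adds a fixed session effect and a random sequence effect. No pre-vaping value, change score or pre/post time term is named.

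Figure 1 (Section D.i) lists at the start of the session "Surveys Respiratory Measures Cardiovascular Measures Blood Draw (0 min", and Table 1 lists the same heart and lung measures at visit 1 and at all later visits. The only later heart and lung entry in Figure 1, at 3 hours after exposure, reads "Respiratory Measures Cardiovascular Measures (Option B Only". Sections D.ii.2.a and D.iii say: "Arterial stiffness, blood pressure, and heart rate will be measured at baseline".

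**The concern.** In a within-person design the random participant effect removes stable differences between people in lung function or vessel tone. It does not remove shifts from one session to the next, such as that day's airway state or probe placement. The pre-vaping value taken in the same session is the measurement that captures these shifts. Gender, the one covariate named, is constant within a person and as a main effect cannot sharpen a comparison of liquids within that person.

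If the pre-vaping value is left out, the whole session-to-session shift stays in the error term. That makes acute effects harder to detect at thresholds of 0.01 and 0.01/6. Leaving the choice open also lets the analyst pick post value, change or adjusted value after seeing the data, and these three can differ noticeably in precision.

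**Working it through.** **Inputs**
- Completers: 60 (Section D.ii: "Utilizing a within-subjects, factorial design, 60 e-cig users (aged 21-25 years) will complete vaping sessions").
- Main-effect threshold: 0.01 (Section E: "we will assume a significance threshold corresponding to one expected false discovery per 100 tests").
- Interaction-cell threshold: 0.01/6 = 0.0017 (Section E.i).
- Effect: 0.5 SD of the paired differences, with 80% power stated for both (Section E.i).
- Not in the documents: whether tests are one- or two-sided (two-sided assumed) and rho, the pre/post correlation left within a person and session after the participant effect (shown as a range).

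**Step 1: the plan's own figure.** Under the normal approximation, power = Φ(d√n − z), with d√n = 0.5 × √60 = 3.873.
- At 0.01: Φ(3.873 − 2.576) = 90.3%; by noncentral t, 88.2%.
- At 0.01/6: Φ(3.873 − 3.144) = 76.7%; by noncentral t, 71.4%.

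The stated 80% is exceeded for main effects, where 51 people would be enough by t-test. It is not reached for interaction-cell pairs, which need 69 by two-sided t-test. A one-sided t-test would give 78.7%.

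**Step 2: effect of adjustment.** Using the pre-vaping value as a covariate multiplies the within-person error variance by 1 − rho², so d becomes 0.5/√(1 − rho²). A simulation with 60 people and eight liquids, adjusting for participant and session, gave variance ratios of 1.00, 0.91, 0.75 and 0.51 at rho 0, 0.3, 0.5 and 0.7. These agree with the formula.

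**Step 3: the change score.** With equal pre and post variances, its error variance is 2(1 − rho) times the unadjusted one, so d becomes 0.5/√(2(1 − rho)). That is worse than no adjustment when rho is below 0.5.

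Power, two-sided t, n = 60:

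| rho | adjusted, 0.01 | adjusted, 0.01/6 | change score, 0.01 | change score, 0.01/6 |
|---|---|---|---|---|
| 0 | 88.2% | 71.4% | 53.4% | 30.2% |
| 0.3 | 91.4% | 77.2% | 72.7% | 49.7% |
| 0.5 | 96.2% | 87.3% | 88.2% | 71.4% |
| 0.7 | 99.6% | 98.0% | 98.9% | 95.0% |

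The adjusted columns at rho 0 equal the unadjusted power. For an interaction-cell pair, adjustment passes 80% at about rho 0.4 (81.7%).

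**Step 4: fewer post-vaping values.** The split between Options A and B is not stated. As an illustration only, if 30 completers had usable post-vaping values, rho = 0.5 would take power from 50% to 66% at 0.01 and from 26% to 40% at 0.01/6. The low starting points come from the missing post-vaping values, not from the missing covariate.

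**Step 5: where a post-vaping value exists.** Option A visits last about 2 hours, so a 3-hour value does not fit them. An Option B visit lasts about 6 hours. Two 35-minute puffing periods, the 3-hour washout and a second 3-hour wait come to 0:35 + 3:00 + 0:35 + 3:00 = 7 h 10 min before any set-up. A post-vaping value may therefore exist only for the first session of each Option B visit. It would fall at the end of the washout, when the second session's pre-vaping value is due.

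**The case against.** The covariate list in Section E is open: gender is only an example. A reader might infer that the plan has decided against adjustment, but the text supports only that adjustment is not specified. That objection stands, and the point is worded accordingly.

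A reader might also infer that omitting the covariate leaves H1b underpowered or biased. The documents do not support this. Main effects have 88% power unadjusted, above the planned 80%. In simulation the unadjusted, adjusted and change-score estimates all averaged the true 0.30. The shortfall for interaction-cell pairs arises from sample size and threshold. Adjustment closes it only if rho is high enough; at 0.3 power is still 77%.

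Nor is adjustment a remedy for carryover in Option B. With 30% same-day carryover and rho 0.5, the unadjusted estimate averaged 0.294 and the adjusted one 0.297 against a true 0.30, a negligible difference. Section E.i already says carryover and period effects will be examined.

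The strongest objection is that only the pre-vaping value is scheduled in every session, so for Option A there may be no outcome to adjust. This also stands. It limits the point to outcomes with a post-vaping measurement and exposes a separate gap in the definition of the outcomes. It does not remove the case for prespecifying the covariate where both values exist. Adjustment also stayed more precise and essentially unbiased in simulation when one value served as the first session's post-value and the second session's pre-value.

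**Conclusion.** The point holds in a limited form. Section E does not specify adjustment for a same-session pre-vaping value that the schedule already collects, and H1b heart and lung contrasts may lose precision where a post-vaping value exists. Over rho 0 to 0.7, the gain with 60 completers is 0 to about 11 percentage points at 0.01 (99.6 − 88.2) and 0 to about 27 at 0.01/6 (98.0 − 71.4).

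These figures assume two-sided t-tests, 60 usable post-vaping values, and an effect stated in SDs of unadjusted paired differences, a scale the plan does not define. The gain shrinks if part of that SD is true person-by-liquid variation, and is already counted if the plan's SD is that of baseline-adjusted values. Fewer post-vaping values lower every power figure. This is a worthwhile efficiency gain and a prespecification gap, not a flaw in validity. The unclear post-vaping schedule may be the larger problem for H1b.

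**What to change.** In Section E, for each respiratory and cardiovascular outcome with a post-vaping measurement:
- Make the post-vaping value the dependent variable.
- Prespecify that session's pre-vaping value as a covariate, split into the participant's mean pre-vaping value and the session's deviation from it.
- Do not use a raw change score.
- For Option B, state whether the first session's 3-hour value also serves as the second session's pre-vaping value.

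This takes a short addition to the text and up to two model terms; the covariate needs no new measurement.

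Separately, reconcile Figure 1, Table 1, the stated visit lengths and the baseline-only wording in Sections D.ii.2.a and D.iii, so that each H1b heart and lung outcome and its time point are defined for both options.
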